Primary Aim: The primary aim of this study is to determine the difference between changes in neurocognitive functioning from baseline to the 6 month follow-up in adult survivors of childhood cancer who are randomized to receive melatonin compared to those randomized to receive placebo. We hypothesize that survivors randomized to the melatonin group will have a greater improvement in neurocognitive functioning than those randomized to the placebo group. We have identified six neurocognitive domains in which the marginal impairment rate is >15% in the SJLIFE cohort. Normalized Z-scores ($M=0$, $SD=1$) are available for each domain and survivors who score at or below the 10th percentile will be classified as impaired on that specific domain. The lowest test-retest correlation coefficient for the neurocognitive measures has been observed to be 0.60. Then, assuming the difference in the Z-scores to be normally distributed but assuming (conservatively) the variance to be 1, we need outcome data for 131 survivors between the melatonin and placebo arms in Cohorts 1 and Group 2 to detect an improvement of .66 units (in standardized scale, considered to be clinically meaningful) with 80% power with type I error control $\alpha=0.05/6=0.0083$ to adjust for multiplicity of 6 tests for each subscale. The analysis for Aim 1 will be completed using a two-sample t-test. Assuming an attrition and loss to follow up of 25%, we plan to enroll 987 survivors (Cohort 1=328; Cohort 2=328; Cohort 3=331).

Protocol MNEMONIC and Title: MIND - Melatonin Intervention for Neurocognitive Deficits in the St. Jude Lifetime Cohort

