2.3 PRELIMINARY STUDIES

Data from ongoing and completed studies by SJCRH researchers further elucidate the association between sleep, fatigue and neurocognitive impairment in adult survivors of childhood cancer. These data underscore the need for interventions that have the potential to ameliorate both neurocognitive and sleep dysfunction in adult survivors of childhood cancer.

2.3.1 Sleep, Fatigue and Neurocognition: Research efforts led by [name] using the Childhood Cancer Survivor Study (CCSS) cohort provide strong evidence for the associations between sleep quality, fatigue and neurocognitive impairment. Participants included 1,426 adult survivors of childhood cancer who were treated before 18 years of age and survived >5 years from their original diagnosis. Among those with fatigue, 53% reported impaired attention and processing speed compared to 15% of those without fatigue. Similarly, 40% of survivors with poor sleep quality had impaired attention and processing speed compared to 16% of those without poor sleep. Multivariable logistic regression models controlling for sex, age, cranial radiation therapy, psychological distress, and household income revealed increased risk for impaired attention and processing speed for survivors with reduced vitality (RR=1.75, 95% CI, 1.33-2.30), fatigue (RR=1.34, 95% CI, 1.13-1.59), daytime sleepiness (RR=1.68, 95% CI, 1.55-1.83), and poor sleep quality (RR=1.23; 95% CI, 1.01-1.49). Reduced vitality (RR=2.01, 95% CI, 1.42-2.86), daytime sleepiness (RR=2.05, 95% CI, 1.63-2.58), and poor sleep quality (RR=1.45, 95% CI, 1.19-1.76) significantly predicted impaired memory. Importantly, the risk for neurocognitive impairment associated with fatigue and sleep disturbance was roughly equivalent to that seen with high-dose cranial radiation.

2.3.2 Actigraphy and Neurocognition: Drs. [name] and [name] recently completed a pilot study examining sleep parameters in relation to specific neurocognitive processes in 35 adult survivors of Hodgkin's disease using the St. Jude Lifetime Cohort (SJLIFE) at SJCRH. Participants were on average 15 years old at the time of their cancer diagnosis (range, 5 to 18 years) and 42 years of age at the time of study completion (range, 34 to 55 years). Survivors completed the Epworth

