3.3 Research Participant Recruitment

Recruitment: The study sample will be recruited from participants in the St. Jude Lifetime Cohort (SJLIFE) at SJCRH. This established survivor cohort includes all individuals diagnosed and treated at SJCRH during childhood who are now 10 or more years from diagnosis and are 18 years of age or older. Cohort participants receive risk-based medical follow-up care during their SJLIFE evaluation. Complete medical and treatment records for all survivors are available for review. Survivors undergo a neurocognitive evaluation as a part of the established SJLIFE parent

protocol. We will recruit survivors who previously underwent neurocognitive evaluation as a part of the parent protocol, as well as survivors who are eligible for future neurocognitive evaluation through SJLIFE.

As of June 6, 2012, 4,287 patients treated at SJCRH are eligible for participation in SJLIFE and 2,809 have agreed to return to the SJCRH campus for a SJLIFE evaluation. We propose to recruit 342 patients from the available sample, 232 with documented neurocognitive impairment and 110 without neurocognitive impairment. Between December 2007 and June 2011 we completed neurocognitive evaluations for 1,183 SJLIFE participants. Of these, 986 have a measured IQ >79 (83%). Sixty percent of patients with IQ >79 had observed impairment in ≥ 1 of the six neurocognitive domains required for inclusion in the current study. Based on sleep data obtained from the Childhood Cancer Survivor Study Cohort, we estimate that approximately 30% of survivors will have delayed sleep onset latency (SOL) ≥ 30 minutes once per week or more frequently. Figure 1 provides a schematic representation of expected study participants eligible for recruitment.

[figure not shown]

Figure 1. Flow diagram of expected study participants eligible for recruitment

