11.0 STATISTICAL CONSIDERATIONS

The primary focus of this study is to evaluate the efficacy of melatonin on neurocognitive functioning in long term survivors of childhood cancer. Currently, there are 2,331 survivors potentially eligible for this study and 1,410 (61% have been identified as expected to have least one area of neurocognitive impairment. Further, it is estimated that among all the eligible survivors roughly 30% will have delayed sleep (sleep onset latency ≥ 30 minutes). Thus, the eligible survivors can be classified into three distinct cohorts (I) Those who are neurocognitively impaired but don't have delayed sleep 987 (II) Those who are neurocognitively impaired and have delayed sleep 423, i.e. 30% of 1,410, and (III) Those who don't have neurocognitive impairment but have delayed sleep problems (this would be roughly 30% (276) of those who are not neurocognitively impaired. Targeted enrollment for the study is 987 survivors and expected evaluable is 395.

[figure not shown]

Figure 2. Three group stratification with parallel allocation to melatonin/placebo

Primary Objective: Examine the efficacy of melatonin treatment on neurocognitive functioning in adult survivors of childhood cancer.

- Hypothesis 1: Long-term survivors of childhood cancer with documented baseline neurocognitive deficits (Cohorts 1 and 2), in attention, memory,

and/or executive functioning, randomized to the melatonin treatment arm, will demonstrate improved neurocognitive performance following six months of treatment compared to those randomized to placebo.

The primary objective of this study is to demonstrate that treatment with melatonin will be associated with improvement in neurocognitive performance. This will be evaluated in Cohorts 1 and 2 independently. The study will be conducted by randomizing survivors to melatonin or placebo within each of the two Cohorts.

For those who are in Cohorts 1 and 2 baseline neurocognitive evaluation along with other evaluations will be obtained prior to randomization to melatonin or placebo arm. After randomization, sleep data will be collected using actigraphy in week one when the survivors are in their homes. The intervention will be delivered for a period of six months with regular phone calls for monitoring. Then one week before the six month visit sleep data using actigraphy will be collected. The neurocognitive data will be collected at the 6 month return visit (post-treatment).

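### The Cohort 3 enrolment target of 331 exceeds the roughly 276 survivors the plan currently counts for that cohort, and does not follow from 133 evaluable at 25% attrition

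*Combined protocol and SAP*

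**What the plan says.** **Pool.** Section 11.0 opens with the eligible population: "Currently, there are 2,331 survivors potentially eligible for this study and 1,410" of these are expected to have at least one area of impairment. It then assumes that "among all the eligible survivors roughly 30% will have delayed sleep", and derives the Cohort 3 pool: "this would be roughly 30% (276) of those who are not neurocognitively impaired".

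**Enrolment target.** The Protocol Summary (Data Analyses, Primary Aim) reads "we plan to enroll 987 survivors (Cohort 1=328; Cohort 2=328; Cohort 3=331"). The reason given is loss of participants: "Assuming an attrition and loss to follow up of 25" per cent. Section 11.0 repeats the total: "Targeted enrollment for the study is 987 survivors and expected evaluable is 395".

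**Other Cohort 3 figures.**
- The Protocol Summary (Sample Size; Secondary Aim 1) uses 133 as the number with outcome data.
- Section 11.0 uses the same 133 as the number to enrol (end of the primary-objective sample-size paragraph) and as the number to randomise (sleep objective).
- Section 3.3 proposes to recruit 342 in all: "232 with documented neurocognitive impairment and 110 without neurocognitive impairment".

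**Sleep power.** Secondary Aim 1 and Section 11.0 call for 131 in Cohort 2 and 133 in Cohort 3 to detect a 15-minute improvement, with SD 27.7 minutes, 80% power, alpha 0.05 and a two-sample t-test.

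**The concern.** An enrolment target should not exceed the population from which the cohort is drawn. Here the total of 987, of which 331 is a part, stands in the same paragraph as the pool of 276. The documents give no larger Cohort 3 count that would support 331.

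Cohort 3 is one of the two groups that test Hypothesis 2, and the only one with delayed sleep onset and no impairment. With 110, 133 and 331 all in the text, anyone tracking accrual, including the DSMB at its six-monthly reviews, cannot tell when Cohort 3 is complete or falling behind. Nor does the plan state a participation rate, so the reader cannot judge whether the 133 evaluable behind the sleep comparison is realistic.

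**Working it through.** **Step 1: reproduce the pool (Section 11.0).**
- Unimpaired: 2,331 − 1,410 = 921.
- With delayed sleep: 0.30 × 921 = 276.3, so the plan's 276 reproduces.

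**Step 2: compare the target with the pool.**
- 331/276 = 1.20, and 331 − 276 = 55.
- Even if everyone counted took part, 331 could not be reached from this count.

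**Step 3: try to reproduce 331 from 133 and 25% attrition.**
- Correct inflation: 133/(1 − 0.25) = 177.3, rounded up to 178.
- Common shortcut: 133 × 1.25 = 166.25, rounded up to 167.
- Neither gives 331. The loss that 331 implies is 1 − 133/331 = 0.598, about 60%. The total shows the same pattern: 395/987 = 0.40.
- Conversely, 331 enrolled with 25% loss would leave 331 × 0.75 = 248 evaluable, far more than 133.

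**Step 4: does 133 evaluable fit in the pool?**
- 133/276 = 48%.
- With 25% loss, 178 must enrol: 178/276 = 64% of the stated pool.

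**Step 5: power for the sleep comparison in Cohort 3.** Two-sample t-test, 1:1, standardised difference 15/27.7, alpha 0.05. Sidedness is not stated for this aim and is taken as two-sided. Evaluable = 276 × uptake × 0.75. The uptake rates are illustrative, because the plan gives none.

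| Uptake of 276 | Enrolled | Evaluable | Power |
|---|---|---|---|
| 40% | 110 | 83 | 68% |
| 50% | 138 | 104 | 78% |
| 60% | 166 | 124 | 85% |
| 64% | 178 | 133 | 87% |
| 100% | 276 | 207 | 97% |

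If all 276 enrolled but only the implied 40% were evaluable (276 × 133/331 = 111), power would be about 81%.

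**Side note on 133.** At two-sided alpha 0.05 the t-test needs 55 per arm, or 110 in all, for 80% power. The figure of 133 reproduces only at two-sided alpha 0.025 (66.1 per arm). At that level, 111 evaluable gives about 72%.

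**The case against.** **The two figures may count different people.** Consent is taken at the campus visit (Section 12.0). Cohorts are assigned only after baseline testing, and participants with neither condition then go off study (Sections 3.6 and 8.1.9). Enrolment could therefore include people who never qualify, and a 40% yield is compatible with screen failure plus attrition. This is a fair possibility, but the plan does not say so. The 331 is labelled as Cohort 3, the only loss named is 25% attrition, and the mailed pre-screening form already asks two sleep questions. If screen failure is meant, its rate has to be stated.

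**The pool can grow.** Section 11.0 describes the current position, and Section 3.3 also recruits survivors eligible for future evaluation. It counts 4,287 eligible for SJLIFE, of whom 2,809 had agreed to return. The 2,331 equals 2,809 × 0.83, the share with IQ above 79, although the plan does not state that derivation. Assuming the same fractions held for all 4,287, the Cohort 3 pool would be 4,287 × 0.83 × (921/2,331) × 0.30, about 422. A reader should therefore not treat 276 as an upper limit. The plan itself makes no such projection, so 331 remains unsupported.

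**The power does not depend on 331.** A reader might infer that the sleep power cannot be delivered. The documents do not support that: the power rests on 133 with outcome data, which fits within 276, and even 111 gives about 81% at two-sided alpha 0.05.

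**The pool cannot be shrunk by formula.** Section 2.3.1 reports that "poor sleep quality (RR=1.45, 95% CI, 1.19-1.76) significantly predicted impaired memory", and a reader might use such ratios to argue that fewer unimpaired survivors have delayed sleep. Those ratios are covariate-adjusted, come from another cohort (CCSS), and concern sleep quality rather than onset latency. They cannot be turned into a Cohort 3 count.

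**Exclusions.** The readable text shows no deduction for Section 3.2, but the Figure 1 flow diagram is not available here. One cannot assert that none was made.

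**Conclusion.** The contradiction holds. The Cohort 3 target of 331 is 120% of the roughly 276 currently counted, does not follow from 133 and 25% attrition (178), and conflicts with the 133 to be enrolled in Section 11.0 and the 110 in Section 3.3. This needs no assumption beyond the plan's own figures, taking the 331 to be Cohort 3 members, as it is labelled.

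The consequence for power is narrower. The 133 evaluable is attainable from 276 if about 64% enrol and loss is 25%, with about 87% power at two-sided alpha 0.05. It is demanding, and nothing in the plan shows it to be realistic: at 50% or 40% uptake, power would be about 78% or 68%. These uptake rates are illustrative. Cohort 3 serves a secondary objective, so the primary comparison in Cohorts 1 and 2 is not affected by this Cohort 3 shortfall.

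**What to change.** 1. In the Protocol Summary (Primary Aim), replace 331 with the number that follows from 133 and the stated attrition, 178. Alternatively, keep a larger number, state the screen-failure and attrition rates behind it, and show that the pool supports it.
2. Carry the result through to the 987 in the Protocol Summary (Sample Size; Primary Aim) and Section 11.0. The 328 for Cohorts 1 and 2 needs the same check: 131/0.75 = 174.7, or 175 each, so 25% attrition throughout gives 175 + 175 + 178 = 528.
3. Reconcile Section 3.3 (342 = 232 + 110) and the Section 11.0 sentence that enrols 133. Say each time whether a figure means enrolled, randomised or evaluable.
4. State the assumed participation rate, whether the 276 is before or after the Section 3.2 exclusions and whether future evaluations are expected to add to it, and the Cohort 3 power this supports at two-sided alpha 0.05.

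The cost is amendment wording and a little arithmetic, plus an estimate of participation and screen failure. No extra patients are needed. The downside is a less favourable stated enrolment figure.

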Secondary Aim 1: The primary interest of secondary aim one is to assess the efficacy of melatonin on delayed sleep onset latency in adult survivors of childhood cancer, which will be evaluated in Cohorts 2 and 3. We hypothesize that survivors randomized to the melatonin treatment arm will evidence a greater reduction in sleep onset latency compared to survivors randomized to placebo. The CCSS cohort mean and SD for sleep onset latency among participants with delayed sleep onset latency (i.e. SOL \geq 30 minutes) is 46.2 and 27.7 minutes, respectively. The test-retest correlation for sleep onset latency from the PSQI has been observed to be in the range of 0.70. Following the justification set forth in the Primary Aim, and assuming the SD to be 27.7, we will need outcome data for 131 survivors in Cohort 2 and 133 in Cohort 3 between the melatonin and placebo arms for these Cohorts to see an improvement of 15 minutes in sleep onset latency with 80% power with type I error control $\alpha=0.05$. The analysis for Aim 2 will be completed using a two-sample t-test.

Secondary Aim 2: The aim of this objective is to investigate the association between sleep onset latency and specific neurocognitive processes [Cohort 2]. We hypothesize that decreased sleep onset latency following 6 months of melatonin treatment will be associated with improved neurocognitive performance. We will need outcome data for 131 survivors in Cohort 2 [66 randomized to melatonin, 65 randomized to placebo] so that we will have 80% power to detect a correlation of at least 0.25 between reduced sleep onset latency and improved neurocognitive performance with type 1 error control $\alpha=0.05$.

Exploratory Aims: To explore the association between endogenous melatonin levels and improvement in sleep onset latency. To explore the association between sleep quality and psychological distress and health related quality of life.

Primary Anticipated Completion Date: [REDACTED]

Anticipated Study Completion Date: [REDACTED]

Timeframe for Primary Outcome Measure: Approximately 6 months

Data Management: Data will be managed by the Neuropsychology Research Team and the Clinical and Survey Research Center in the Department of Epidemiology and Cancer Control and the Department of Nursing Research. Statistical analysis will be provided by the Biostatistics Department at St. Jude Children's Research Hospital.

Human Subjects:

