There are 10 subscales on which a survivor could be impaired and, out of 10 such subscales, we have identified six in which the marginal impairment rates were seen to be greater than 15%. There are normalized Z-scores available for each subscale and a survivor that falls below the 10% (≤ -1.3) is classified as impaired on that subscale. It is possible that a survivor could be impaired on more than one subscale but we will assess improvement in each subscale independently. Thus, we will have the Z-score corresponding to each of the subscales within at baseline and at follow-up visit. For simplicity, consider the first subscale. We don't expect to see any change in the Z-scores for the placebo arm but we do expect to see an improvement in the melatonin arm. Let Z_{1m}^1 and Z_{2m}^1 denote the Z-scores at baseline and follow-up time points for the first subscale on melatonin arm and let Z_{1p}^1 and Z_{2p}^1 denote the Z-scores at baseline and follow-up time points for the first subscale in the placebo arm. Let $Z_{DM}^1 = Z_{2m}^1 - Z_{1m}^1$ and $Z_{DP}^1 = Z_{2p}^1 - Z_{1p}^1$ denote the difference between the two time points in the two arms. Then our interest is in testing the null hypothesis $H_0: \mu_{Z_{DM}^1} = \mu_{Z_{DP}^1}$ vs $H_1: \mu_{Z_{DM}^1} \neq \mu_{Z_{DP}^1}$ i.e. the mean of the difference scores for the first subscale would be same for the two arms vs. they will be different. The lowest test-retest correlation coefficient for the neurocognitive measures has been observed to be 0.60. Then, assuming the difference in the Z-scores to be normally distributed but assuming (conservatively) the variance to be 1, we will need to randomize 131 survivors between the melatonin and placebo arm to detect an improvement of 0.66 units (in standardized scale, considered to be clinically meaningful) with 80% power with type I error control $\alpha=0.05/6=0.0083$ to adjust for multiplicity of 6 tests for each subscale. However, the sample size required to evaluate the secondary objective in cohorts 2 and 3 is 131 and 133, respectively, per cohort. Thus, we plan to enroll 131 research participants from Cohorts 1 and 2 and 133 research participants from Cohort 3.

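### The printed alpha, power and sample size do not agree: at 0.0083 and 0.05, 131/131/133 evaluable give about 86-87% power, not 80%, so the error is on the conservative side

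*Combined protocol and SAP*

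**What the plan says.** Section 11.0, Primary Objective, assumes a 0.66-unit improvement in Z-score change with variance 1 and a two-sided alternative: "we will need to randomize 131 survivors between the melatonin and placebo arm to detect an improvement of 0.66 units", "with 80% power with type I error control $\alpha=0.05/6=0.0083$ to adjust for multiplicity of 6 tests for each subscale". The Protocol Summary (Data Analyses, Primary Aim) names the two-sample t-test and describes the same 131 as evaluable: "we need outcome data for 131 survivors between the melatonin and placebo arms in Cohorts 1 and Group 2".

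For sleep onset latency (15 minutes, SD 27.7, alpha 0.05, 80% power, two-sample t-test) the Summary says "we will need outcome data for 131 survivors in Cohort 2 and 133 in Cohort 3 between the melatonin and placebo arms". Section 11.0 gives the same inputs and calls these sizes required: "However, the sample size required to evaluate the secondary objective in cohorts 2 and 3 is 131 and 133, respectively, per cohort". It then concludes: "Thus, we plan to enroll 131 research participants from Cohorts 1 and 2 and 133 research participants from Cohort 3".

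On how the cohorts are used, Section 11.0 says of the primary objective: "This will be evaluated in Cohorts 1 and 2 independently". On totals: "Targeted enrollment for the study is 987 survivors and expected evaluable is 395". Other counts remain elsewhere. Section 3.3 has 342, made up of 232 and 110. The Section 11.2 table has 232 (primary) and 226 (sleep), beside 131 and 395.

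**The concern.** Once effect, SD, alpha, power and test are fixed, the minimum N follows. The printed N is too large for the printed alpha and power in both calculations. Cohorts 2 and 3 also share identical sleep inputs, so they cannot require two different sizes.

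The direction is safe for power. What is at stake is which design the text describes. One candidate uses the printed thresholds and has spare power. The other uses stricter, unprinted thresholds and has 80%. They set different bars for declaring success on the primary outcome, and choosing between them after seeing results would be data-driven.

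**Working it through.** **Inputs.** Primary: δ = 0.66, σ = 1, α = 0.05/6, two-sided (Section 11.0). Sleep: δ = 15, σ = 27.7, α = 0.05 (Section 11.0); sidedness is not printed, so two-sided is assumed, following Aim 1. Allocation is 1:1 (Section 3.6), so 131 splits 66/65 and 133 splits 67/66.

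**Formula.** Noncentrality λ = δ / (σ√(1/n₁ + 1/n₂)); power = P(T > t-critical), where T is noncentral t with n₁ + n₂ − 2 degrees of freedom.

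**The plan's own figures do not reproduce at the printed alphas.**

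| Comparison | N | λ | t-critical | Power |
|---|---|---|---|---|
| Primary, α 0.05/6 | 131 | 3.777 | 2.680 | 86.2% |
| | 116 | 3.554 | 2.685 | 80.6% |
| | 115 | 3.539 | 2.685 | 80.1% |
| | 114 | 3.523 | 2.686 | 79.7% |
| Sleep, α 0.05 | 133 | 3.122 | 1.978 | 87.3% |
| | 131 | 3.099 | 1.979 | 86.8% |
| | 110 | 2.840 | 1.982 | 80.4% |

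The minimum is 115 for the primary aim (116 with equal arms) and 110 for sleep. At the printed N, 80% power corresponds to 0.62 units rather than 0.66, and to 13.7 and 13.6 minutes rather than 15.

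**Possible explanations at the printed alphas.**
- Normal approximation, n per arm = 2(z₁₋α/₂ + z₀.₈)²σ²/δ². Primary: 2(2.638 + 0.842)²/0.66² = 55.6, or 112 in total. Sleep: 2(1.960 + 0.842)²(27.7/15)² = 53.5, or 108. Both are further from 131/133.
- One-sided sleep test at 0.05: 86 in total, further still.
- Variance implied by a test-retest correlation of 0.60: 2(1 − 0.60) = 0.8, giving 93.7% primary power at 131. The gap widens.
- Attrition: the Summary counts 131 and 133 as survivors with outcome data and applies the 25% allowance afterwards. Also 131/116 is +13% and 133/110 is +21%, so no single inflation fits.
- Hypothesis 3 (r = 0.25, α 0.05, Fisher z): N = ((1.960 + 0.842)/0.2554)² + 3 = 123.3, so 124. At 131 power is 82.4%.

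**Total need at the printed inputs.** Cohort 2 must also serve Hypothesis 3, and 116 would give it only 77.5%. The need is therefore 116 + 124 + 110 = 350 (349 using 115). Against 395 this leaves 45-46 more than needed, about 13%.

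**Alternative count analysis in Section 11.0** (65-67 per arm, α 0.05, roughly 90% stated). Variances are 6(0.05)(0.95) = 0.285 and 6(0.12)(0.88) = 0.634. Normal-approximation power is Φ(0.42/√(0.9186/n) − 1.960) = 94.2% at 65 and 94.8% at 67; simulated Welch tests give 94.3-95.1%.

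**What does reproduce 131 and 133.** At α = 0.05/12, 131 gives 80.3% and 130 gives 79.9%. At α = 0.025, 133 gives 80.3%, 132 gives 79.9% and 131 gives 79.6%. The count analysis at 0.025 gives 90.2-91.1% with 65-67 per arm.

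**Error rates, if tests are independent.** Six tests at 0.05/6: 1 − (1 − 0.05/6)⁶ = 4.9%. Twelve: 9.6%. Two sleep tests at 0.05: 1 − 0.95² = 9.75%.

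**The case against.** The strongest reply is that 131 and 133 are merely sufficient rather than minimal. If they are reached, the trial exceeds its stated power, and no test, estimate or participant burden changes. That stands as to direction and limits the severity. It does not rescue the text, which calls these sizes needed and required for 80% power.

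Three stronger readings are tempting.

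- A reader might infer that the true total need is 342, because 116 + 116 + 110 matches Section 3.3, and 232 and 226 in Section 11.2 match 116 + 116 and 116 + 110. The match suggests leftover counts from a smaller design, but 342 leaves Hypothesis 3 short in Cohort 2.
- A reader might infer that N was resized with alpha halved for two cohorts. Three printed figures fit this: 131, 133 and the roughly 90% for the count analysis. It is probable but remains an inference. No section prints 0.05/12 or 0.025, and the 90% would also fit 55-58 per arm (half of 110 and 116) at the printed 0.05.
- A reader might take "This will be evaluated in Cohorts 1 and 2 independently" as settling that claims are per cohort with no cross-cohort adjustment or, conversely, charge the plan with nearly 10% error. Neither follows. Section 11.0 uses the same adverb for the subscales and still divides alpha by 6, while Hypotheses 1 and 2 each name two cohorts in one statement. Equally, no section adopts a rule that success in either cohort suffices.

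**Conclusion.** The concern holds as a conservative mismatch of alpha, power and N. At the printed alphas, power is 86.2% (primary), 86.8% (Cohort 2 sleep) and 87.3% (Cohort 3 sleep), against a stated 80%, and the count analysis has about 94-95% against roughly 90%. This rests on the plan's own effects and SDs, a two-sided t-test (assumed for sleep) and 131/131/133 actually being evaluable; whether those counts can be reached is a separate question. It is not a finding of underpowering or of uncontrolled type I error. It should be corrected because the text leaves open which thresholds the design was built on and how results in two cohorts bear on one hypothesis.

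**What to change.** Before unblinding, the sponsor should confirm which alphas generated 131 and 133.

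- **If 0.0083 and 0.05 stand:** in the Protocol Summary and Section 11.0, state about 86% power for the primary aim, about 87% for sleep and about 94-95% for the count analysis. Describe 131/131/133 as the planned evaluable sample size rather than as needed or required.
- **If halved alphas were intended:** print 0.05/12 and 0.025 by amendment, with power 80.3% (primary), 79.6% (Cohort 2 sleep) and 80.3% (Cohort 3 sleep). This changes the decision rule and is more than a wording correction.
- **In either case:** add one sentence saying whether claims are made per cohort or on success in either cohort. At the printed alphas, an either-cohort rule would allow up to 9.6% (primary) or 9.75% (sleep) error if the tests are independent.
- **Counts:** in Section 11.0, change the wording that has 131/133 randomized or enrolled to evaluable, since the enrolment targets are 328/328/331. In Section 11.2, change 232 to 262 (131 + 131) and 226 to 264 (131 + 133). In Section 3.3, reconcile 342/232/110 with 987 enrolled and 395 evaluable.

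The cost is corrected figures and one sentence, plus an amendment only if the alphas change. No participants, visits or data are added.

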In addition to analyzing the differences for each subscale we will also analyze the data in an alternative manner as follows. For each subscale an improvement will be defined if the difference in the Z-score (follow-up time point – baseline) is greater than 0.6 units (≥ 0.6). Let us assume that the probability of observing an improvement in a subscale in an individual in the placebo group is about 5% and then the total of 6 subscales (assuming them to be independent with the same probability of improvement) will follow a Binomial distribution $B(6, 0.05)$ with a mean of 0.3 and SD of 0.54. If we assume that the probability of improvement to be higher say about 12% in the melatonin group then the total score in that group will follow a Binomial distribution $B(6, 0.12)$ with a mean of 0.72 and SD of 0.80. Then, we will use two-sample Behrens-Fisher t-statistic to compare the two means. With a sample size of between 65 and 67 in each group we will have roughly 90% power to detect a difference of 0.42 units with type I error control $\alpha=0.05$.

Secondary Objective: Evaluate the efficacy of melatonin treatment on delayed sleep onset latency in long-term childhood cancer survivors.

- Hypothesis 2: Long-term survivors of childhood cancer with delayed sleep onset latency at baseline (Cohorts 2 and 3), randomized to the melatonin treatment arm, will demonstrate improved sleep onset latency following six months of treatment compared to the placebo groups.

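### The 5% placebo improvement rate in the alternative primary analysis does not fit the plan's own change-score model, which implies about 25–27%, so the stated power for a 0.42 difference needs restating

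*Combined protocol and SAP*

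**What the plan says.** Two consecutive parts of Section 11.0 describe the same quantity, the follow-up minus baseline Z-score on a subscale.

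**Sample-size paragraph for the primary objective.** For placebo it says "We don't expect to see any change in the Z-scores for the placebo arm". On variability it says "The lowest test-retest correlation coefficient for the neurocognitive measures has been observed to be 0.60", and it then takes the change as normal, "assuming (conservatively) the variance to be 1". The sample size is set "to detect an improvement of 0.66 units (in standardized scale, considered to be clinically meaningful) with 80% power".

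**Alternative analysis, immediately after.** Each subscale is classed as improved if its change reaches 0.6 Z, and the six results are added up. The placebo rate is introduced by "Let us assume that the probability of observing an improvement in a subscale in an individual in the placebo group is about 5" (per cent) and the melatonin rate by "If we assume that the probability of improvement to be higher say about 12% in the melatonin group". The subscales are combined "assuming them to be independent with the same probability of improvement", giving binomial counts with mean 0.3 and SD 0.54 on placebo and mean 0.72 and SD 0.80 on melatonin. An unequal-variance t-test at alpha 0.05 compares them: "With a sample size of between 65 and 67 in each group we will have roughly 90% power to detect a difference of 0.42" units. No source is given for either rate, and neither is linked to the change-score model above.

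**The concern.** Once a distribution is given for the change score, the share of placebo participants passing a 0.6 cut follows from it and is no longer free to be assumed. A mean of zero with an SD near 1 puts far more than 5% of people above 0.6 through retest variation alone.

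The placebo rate fixes both the expected placebo count and its variance, and hence the power for any given difference in counts. If 5% is too low, the placebo SD of 0.54 is too small and the power stated for 0.42 is too high. A reader of the results would also be surprised to find far more improved subscales on placebo than the plan led them to expect.

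**Working it through.** **Inputs from Section 11.0.** Cut 0.6; placebo mean change 0; change variance 1; lowest retest correlation 0.60; target gain 0.66; six independent subscales; alpha 0.05. Arms of 65 (placebo) and 66 (melatonin) are used, within the stated 65 to 67. The test's sidedness is not stated; two-sided is assumed. Power is by normal approximation, Φ(difference/SE − 1.96), with SE = √(v0/65 + v1/66) and v = 6p(1−p).

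**1. The plan's own figure.**
- Placebo: mean 6 × 0.05 = 0.30; SD √(6 × 0.05 × 0.95) = 0.534.
- Melatonin: mean 6 × 0.12 = 0.72; SD √(6 × 0.12 × 0.88) = 0.796.
- SE = √(0.285/65 + 0.634/66) = 0.118; 0.42/0.118 = 3.55; power = Φ(1.59) = 94%.

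The means and SDs agree with the plan (0.534 is given as 0.54), and the computed power exceeds the 90% stated. The calculation is sound given its inputs.

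**2. Placebo rate implied by the sample-size paragraph.** Rate = 1 − Φ(0.6/SD). With unit-variance scores and retest correlation r, SD = √(2(1−r)).

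| Change model | SD | Placebo rate | Mean count of 6 |
|---|---|---|---|
| Variance 1 (plan) | 1 | 27.4% | 1.65 |
| r = 0.60 (plan's lowest) | 0.894 | 25.1% | 1.51 |
| r = 0.80 (assumed) | 0.632 | 17.1% | 1.03 |
| r = 0.90 (assumed) | 0.447 | 9.0% | 0.54 |
| Stated in the plan | – | 5% | 0.30 |

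**3. What 5% would require.** SD = 0.6/1.645 = 0.365, so r = 1 − 0.365²/2 = 0.93, on every subscale if they share one rate. On that SD, 12% on melatonin corresponds to a mean gain of 0.6 − 1.175 × 0.365 = 0.17 Z.

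**4. Power for 0.42 with the placebo rate from step 2.** A difference of 0.42 in the count is 0.07 per subscale.
- Variance 1: 27.4% vs 34.4%, a 0.20 Z shift. SDs 1.093 and 1.164; SE 0.197; 0.42/0.197 = 2.13; power 57%.
- r = 0.60: 25.1% vs 32.1%, a 0.18 Z shift. SDs 1.062 and 1.144; SE 0.193; 0.42/0.193 = 2.18; power 59%.
- Assumed r = 0.80: 68%. Assumed r = 0.90: 85%.

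**5. Difference detectable with 90% power.**
- Variance 1: melatonin rate 38.2%, difference 6 × (0.382 − 0.274) = 0.65, a 0.30 Z shift on all six subscales.
- r = 0.60: melatonin rate 35.7%, difference 6 × (0.357 − 0.251) = 0.63, a 0.27 Z shift on all six.

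**6. Power for the plan's target of 0.66 Z.** The rate on an affected subscale is 1 − Φ(−0.06/SD), which is 52.4% (variance 1) or 52.7% (r = 0.60). Unaffected subscales keep the placebo rate.

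| Subscales gaining 0.66 Z | Variance 1 | r = 0.60 |
|---|---|---|
| 1 | 25% | 31% |
| 2 | 73% | 82% |
| 3 | 97% | 99% |
| 6 | >99.9% | >99.9% |

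**7. One common probability.** Cohorts 1 and 2 enter on at least one score at or below the 10th percentile (Section 3.6). Regression to the mean lifts a subscale selected for being low more than one that was not. Illustration, on assumed unit-variance normal scores with 15% marginal impairment and r = 0.60: about 51% of impaired and 21% of non-impaired subscales would pass the cut on placebo.

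**The case against.** The paragraph is openly conditional. Its rates are offered as assumptions, it states independence and equal probability, and its figures follow from them, with power a little better than claimed. That stands: there is no arithmetic error here.

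The sample-size paragraph calls variance 1 conservative, and 0.60 is the lowest retest correlation, so more reliable tests would bring the placebo rate down. That also stands, and 25–27% should be read as an upper-end figure before any effect of selection. But even an assumed 0.90 leaves 9%, and nothing in the documents supports the 0.93 that 5% requires.

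The 57–59% figure takes the 0.42 difference from one paragraph and the placebo rate from the other, a pair the plan never proposes. On the model-based rate, 0.42 is only a 0.18–0.20 Z shift, under a third of 0.66. This is fair. The figure shows that the power statement does not carry over to the model-based placebo rate; it does not show that the analysis fails for the effect of interest.

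A reader might infer that 12% on melatonin contradicts the 0.66 Z target, since a mean gain above the cut puts more than half past it. The documents do not support this as a contradiction: the alternative paragraph never ties 12% to 0.66 Z, and a supplementary analysis may be powered for a smaller effect. What is missing is a statement of which effect was meant.

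**Conclusion.** The point holds as an inconsistency of assumptions. The sample-size paragraph's change model gives a placebo improvement rate of about 25–27% per subscale, against the stated 5%, and a mean placebo count of 1.5–1.65, against 0.3. With that rate, power for a 0.42 difference is about 57–59% instead of roughly 90%, and 90% power needs a difference of about 0.63–0.65. These results rest on a normal change score, independent subscales, two-sided alpha 0.05 and 65 versus 66 per arm.

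A reader might go further and infer that the alternative analysis is underpowered. The documents do not support that: for 0.66 Z on three or more independent subscales, power is 97% or higher. It falls below 90% if only one or two respond.

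A reader might also try to size the selection effect by dividing the 15% marginal impairment rate by the 60% impaired on at least one measure in Section 3.3. The first is described for the SJLIFE cohort and the second for those with IQ above 79, so the ratio is not a reliable bound. The main result does not need it.

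The consequence is limited. This is a supplementary analysis; neither the sample size nor the primary t-tests depend on these rates.

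**What to change.** Rewrite the alternative-analysis paragraph in Section 11.0:

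- Derive the placebo rate, the count means and SDs, and the difference detectable with 90% power from a change model consistent with the sample-size paragraph. Otherwise, cite retest data that support 5% (change SD about 0.365, correlation about 0.93).
- State the Z effect behind the melatonin rate and the number of subscales on which it is assumed.
- Note that selection on low baseline scores means impaired and non-impaired subscales do not share one improvement probability.
- Note that positive correlation between subscales lowers power below the figure obtained under independence.

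The cost is one paragraph of text and a short recalculation. Sample size, primary t-tests and data collection do not change.
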